4.1 Primary Efficacy

The primary efficacy endpoint is pelvic recurrence rate at 3 years.

4.2 Secondary Efficacy

The secondary efficacy endpoints are:

- Pelvic relapse free survival (PRFS)
- Extra-pelvic relapse free survival (EPRFS)
- Relapse free survival (RFS)
- Overall survival (OS)
- Rate of sentinel node detection
- Rate of parametrial involvement
- Rate of surgical margins involvement
- Rate of pelvic nodes involvement
- Patient reported outcomes (using EORTC QLQ-C30 with module QLQ-CX24, FSFI and FSDS-R)

4.3 Safety

The safety endpoints are serious and non-serious adverse events, other safety events during the surgeries and follow-up.

5. Sample Size and Power

It was estimated that 3-year pelvic recurrence rate for the radical hysterectomy is around 4% and the non-inferiority of the simple hysterectomy to radical hysterectomy would be claimed if its 3-year pelvic recurrence rate is 8% or lower. In the original protocol with pelvic relapse free survival (PRFS) as the primary endpoint, this is equivalent to claim the non-inferiority of the simple hysterectomy to radical hysterectomy when a hazard ratio in PRFS of simple hysterectomy to radical hysterectomy is less than or equal to 2.04. In order to conclude the non-inferiority at 0.05 level with 80% power when PRFS is the same in the two arms, a total of 49 pelvic relapses would be required before the final analysis is performed. Assuming that enrollment rate is 200 patients/year and all patients would be followed for additional 3.5 years after the last patient randomized, enrollment of 700 patients in 3.5 years was required to observe the required number of pelvic relapses at the time of final analysis.

With 350 patients enrolled in each arm, the study would have 85% power to conclude the non-inferiority based on a margin of 4% in the revised primary endpoint, i.e., 3-year pelvic recurrence rate, at $\alpha=0.05$ when the pelvic recurrence rate at 3 years is assumed the same in the two arms.

6. Data Set Descriptions

Three types of analysis samples will be used:

Intention-to-treat Patients:

All patients who have been randomized in the study with the treatment arm being as randomized.

Per-protocol Patients:

All eligible patients who have received hysterectomy, except those who were found to have more advanced stages of cervical cancer on sentinel node mapping, pelvic node dissection or other intraoperative findings consistent with pelvic disease, with the treatment arm being as actually treated.

All Treated Patients:

All patients who have been have received hysterectomy with the treatment arm being as actually treated.

7. Statistical Analysis

7.1 General Methods

Continuous and ordinal categorical variables are summarized using the mean with standard deviation or median with minimum and maximum values and, when appropriate, compared using the Wilcoxon test. Discrete variables are summarized with the number of proportion of subjects falling into each category and compared using Fisher's exact test when appropriate. Time to event variables are summarized using Kaplan-Meier plots. Primary estimates of the treatment differences are obtained with the hazard ratios and confidence intervals from stratified Cox regression models using treatment arm as the single factor. All confidence intervals are computed based on normal approximations except those for rates, which will be computed based on the exact method.

Percentages given in the summary tables will be rounded and may therefore not always add up to exactly 100%. Listings, tabulations, and statistical analyses will be carried out using the SAS (Statistical Analysis System, SAS Institute, North Carolina, USA) software.

Unless otherwise specified, date of randomization and stratification factors will be taken from the Centralized Randomization File.

Baseline evaluations will be those collected on CRF ELIGIBILITY WORKSHEET and BASELINE REPORT and closest to, but no later than, the first day of study treatment for treated subjects and closest to, but no later than, the date of randomization, for subjects who were randomized but who never received treatment.

Laboratory results, adverse events, and other symptoms are coded and graded using the NCI CTCAE when available.

When converting a number of days to other units, the following conversion factors will be used:

1 year = 365.25 days

1 month = 30.4375 days

When either day or month of a date is missing, the missing day and/or month will be imputed by the midpoint within the smallest known interval. For example, if the day of the month is missing for any date used in a calculation, the 15th of the month will be used to replace the missing day. If the month and day of the year are missing for any date used in a calculation, the first of July of the year will be used to replace the missing date.

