- 5.1.7 Patients fluent in English or French must be willing to complete the Quality of Life Questionnaire. The baseline assessments must be completed within 6 weeks prior to randomization. Inability (illiteracy in English or French, loss of sight, or other equivalent reason) to complete the questionnaires will not make the patient ineligible for the study. However, ability but unwillingness to complete the questionnaires will make the patient ineligible. As additional GCIG groups join the study, more translations of some of the questionnaires may be added.

Patients fluent in English or French who reside in Canada and the United Kingdom must agree to participate in the economic evaluation component of this trial and complete the Health Economics Questionnaire. Similarly, patients fluent in English or French accrued from other GCIG groups who are participating in the economic evaluation must be willing to complete the Health Economics Questionnaires.

- 5.1.8 Patient consent must be appropriately obtained in accordance with applicable local and regulatory requirements. Each patient must sign a consent form prior to enrolment in the trial to document their willingness to participate.
- 5.1.9 Patients must be accessible for treatment and follow-up. Investigators must assure themselves the patients randomized on this trial will be available for complete documentation of the treatment, adverse events, and follow-up.
- 5.1.10 Surgery is to be done within 20 weeks of initial diagnosis (NO EXCEPTIONS). The 20-week period includes time required for diagnosis, referral, diagnostic staging, randomization and scheduling of the surgical procedure.
- 5.1.11 Patients must be ≥ 18 years old.

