8.0 TREATMENT PLAN

Although the Canadian Cancer Trials Group acts as the coordinating agency for the trial, the responsibility for treatment of patients rests with the individual investigator. Specific details related to trial conduct by each participating GCIG group are included in the Group-Specific Appendix provided by each Group.

After randomization, protocol-assigned surgery must take place within 8 weeks.

Regardless of when the patient is randomized, protocol surgery must be performed within 20 weeks of the date of the initial pathologic diagnosis (NO EXCEPTIONS). A schema of the treatment plan is shown below.

The decision regarding the use of SN lymph node mapping must be made at the time of randomization.

* Regardless of treatment assignment, surgery will include pelvic lymph node dissection with optional sentinel lymph node (SN) mapping. If SN mapping is to be done, the mode is optional, but the laparoscopic approach is preferred.

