APPENDIX IV - DOCUMENTATION FOR STUDY

Follow-up is required for patients from the time of randomization and will apply to all eligible patients.

This trial will use a web-based Electronic Data Capture (EDC) system for all data collection except the quality of life questionnaire, sexual health questionnaire and the health economics questionnaire. For details of accessing the EDC system and completing the on-line Case Report Forms please refer to the “CCTG EDC Generic Data Management Guidebook” posted on the CX.5 area of the CCTG web-site (www.ctg.queensu.ca).

The electronic CRFs to be used in this trial, through the EDC system, are as follows:

Electronic Folder	Required	To be completed electronically	De-Identified Supporting Documentation Required ¹
Eligibility Checklist	Prior to randomization	At the time of randomization	
Baseline Report	Prior to protocol surgery	Within 6 weeks after randomization	
 • Consent form signature pages (Canadian patients only) • Copies of pathology reports (from initial diagnosis and LRP review) and radiology reports² • PROs³
LEEP/cone/biopsy Checklist			
Surgery Report	4-6 weeks after protocol surgery	Within 8 weeks after surgery	
 • Operative report • Pathology report • Photograph of hysterectomy specimen for surgical QA⁴ • Lymphocintogram and photographs for SN mapping QA⁵
Adjuvant Therapy Report	Upon the completion of adjuvant therapy	Within 8 weeks after the completion of adjuvant therapy	--
Follow-Up Report	Year One – q 3 monthly ⁶ Year Two – q 4 monthly Year Three – q 6 monthly Then q 12 months until study closure. ⁷	Within 8 weeks of the visit date	
 • Pelvic exam notes • Radiology reports (if done) • Pathology/cytology/surgical reports (if done) • PROs³
Recurrence Report	At the time of first pelvic and/or extra-pelvic disease recurrence	Within 8 weeks of the date of recurrence	
 • Pelvic exam notes • Radiology reports (if done) • Pathology/cytology/surgical reports (if done) • PROs³
Short Follow-up Report	q 6 monthly from the date of the most recent recurrence	Within 8 weeks of the visit date	
 • Pelvic exam notes (if done) • Radiology reports (if done) • Pathology/cytology/surgical reports (if done)
Death Report	At the time of patient death	Within 8 weeks of patient death	Autopsy report (if done)

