7.8 Patient Reported Outcomes

The patient report outcomes (PROs) of patients in this study include the quality of life assessed by using EORTC QLQ-C30 (version 3.0) with module QLQ-CX24 and sexual health by the Female Sexual Function Index (FSFI) and the Female Sexual Distress Scale (FSDS-R) before randomization (baseline), at 3 months, 6 months, 12 months, 24 months, 36 months after the surgery but before the first pelvic recurrence, and at the time of the first recurrence. The following are the scoring algorithms for EORTC QLQ-C30, EORTC QLQ-CX24, FSFI and FSDS-R with Q_i denoting the i -th question in the PRO questionnaire.

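### SAP 7.1 sets the baseline cut-off for treated women at surgery, while the protocol and SAP 7.8 set it at randomization, so a late questionnaire answered with the arm known could count as baseline

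*SAP*

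**What the plan says.** SAP 7.1 names the source forms: "Baseline evaluations will be those collected on CRF ELIGIBILITY WORKSHEET and BASELINE REPORT". It then gives a selection rule with two branches. For treated women the value is the one "closest to, but no later than, the first day of study treatment for treated subjects". For the others it is the one "closest to, but no later than, the date of randomization, for subjects who were randomized but who never received treatment".

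The other texts use randomization for everyone. Protocol 5.1.7 says of the questionnaires: "The baseline assessments must be completed within 6 weeks prior to randomization". Protocol 6.0 repeats that six-week window and asks for baseline adverse events within 14 days before randomization. Appendix I puts all these items in its pre-randomization column. SAP 7.8 gives the PRO schedule as "before randomization (baseline), at 3 months, 6 months, 12 months, 24 months, 36 months after the surgery".

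Three further provisions matter:
- Protocol 4.0 describes the trial as non-blinded.
- Protocol 8.0 states: "After randomization, protocol-assigned surgery must take place within 8 weeks".
- SAP 7.8.2 limits PRO analyses to treated women, and SAP 7.8.4 compares the arms on change from baseline, by Wilcoxon test at each time point and by linear mixed model over time.

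**The concern.** A baseline should be fixed before the patient can be influenced by her allocation. Under the treated branch of 7.1, a questionnaire dated between randomization and surgery qualifies. If an earlier one also exists, the later one is preferred because it is closer to surgery. A woman who knows which operation she will have may answer questions on sexual distress or symptoms differently, and differently by arm. Her change scores would then carry an effect of knowing the allocation as well as the effect of the operation.

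At stake is the validity of individual PRO change scores, including those for the Female Sexual Distress Scale-Revised (FSDS-R), which protocol 2.5.4 makes the primary outcome of the sexual health analyses. There is also a practical problem: whoever programs the analysis has two written rules and no instruction on which to follow.

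**Working it through.** The plan states no figure on this point, so there is none to reproduce. The check compares the texts and then sets out the arithmetic of any bias.

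**1. Cut-off dates side by side**

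| Source | Applies to | Latest date allowed for baseline |
|---|---|---|
| SAP 7.1, first branch | treated women | day of surgery |
| SAP 7.1, second branch | never-treated women | randomization |
| SAP 7.8 | PROs | before randomization |
| Protocol 5.1.7 and 6.0 | PROs | before randomization, within 6 weeks |
| Protocol 6.0 | baseline adverse events | before randomization, within 14 days |

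The first row differs from all the others. The interval it adds runs from randomization to surgery, up to 8 weeks under protocol 8.0.

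**2. Which branch could reach the PROs.** SAP 7.8.2 restricts the PRO data set to treated women, so only the first branch, the one that conflicts, could apply.

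**3. Whether a questionnaire can fall in that interval.** None is scheduled there. SAP Table 42 and the questionnaire cover sheets show one named time point before surgery, and it is before randomization. Late completion is still possible. Protocol Appendix VI allows a missed questionnaire to be mailed or taken by telephone and does not exclude the baseline one. The Sexual Health questionnaire is an optional component (protocol 6.0, note 6), so the eligibility condition in 5.1.7 does not clearly force it to be done before randomization.

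**4. Size.** Let *f* be the share of analysed women whose baseline is dated after randomization. Let *b* be the difference between arms, in points, that knowing the allocation creates in those baselines. Then

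shift in the between-arm difference in change = *f* × *b*.

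The documents give neither input, so these values are assumptions:
- *f* = 0: shift 0.
- *f* = 5%, *b* = 1: 0.05 × 1 = 0.05 point.
- *f* = 10%, *b* = 3: 0.10 × 3 = 0.3 point.
- *f* = 20%, *b* = 5: 0.20 × 5 = 1.0 point.

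For scale, protocol 14.6 plans to detect 5 points on FSDS-R. If the protocol schedule was followed, *f* is near zero and so is the shift.

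**5. What is not reached.** Pelvic relapse-free survival, from which the 3-year pelvic recurrence rate is estimated, runs from randomization (SAP 7.5.1). Stratification factors come from the randomization file (SAP 7.1). The 7.1 rule could alter baseline symptom grades in SAP Table 11, but these are descriptive and feed no change score.

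**The case against.** The strongest reply is that the specific rule governs the general one: SAP 7.8 deals with PROs and already places their baseline before randomization. It can be added that 7.1 may not reach PROs at all. Protocol Appendix IV keeps the questionnaires out of electronic data capture and has them uploaded as supporting documents, so they are arguably not collected on the Baseline Report. Protocol 5.1 also allows no exceptions to eligibility, and 5.1.7 ties willingness and the baseline window to it for women fluent in English or French.

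Much of this stands. It makes late baselines uncommon and makes 7.8 the natural reading. It does not close the gap. SAP 7.8 states a schedule, whereas 7.1 is the only text that says how a baseline value is chosen. Appendix IV does attach the PROs to the Baseline Report that 7.1 names. No text says what to do with a questionnaire dated after randomization.

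Four stronger readings are tempting, and the documents do not support them:
- A reader might infer that all change scores are compromised. Only those with a late or repeated baseline questionnaire could be.
- A reader might take the Appendix IV entry for the Baseline Report, "Prior to protocol surgery", as permission to collect questionnaires after allocation. It is the due time of a form. The same row asks for consent signature pages and initial pathology reports, which predate randomization.
- A reader might infer a particular loss of power. That needs both *f* and *b*, and neither is given.
- A reader might infer that the split between treated and untreated women distorts the PRO comparison. PRO analyses use treated women only, so one branch applies throughout.

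**Conclusion.** The inconsistency is real and minor. SAP 7.1 allows a post-allocation value as baseline for treated women, contrary to the protocol and to SAP 7.8, and no order of precedence is stated. The practical effect is confined to PRO change scores of women whose questionnaire was late or repeated. The likely number is small and may be zero, which rests on the assumption that centres followed the protocol schedule. The direction and size of any bias cannot be derived from the documents. The primary endpoint is not affected.

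**What to change.** In SAP 7.1, replace the two-branch rule with one: for all patients, treated or not, baseline is the last evaluation on or before the date of randomization, with a cross-reference to 7.8 for PROs. In SAP 7.8, add three steps:
- Report, by arm and questionnaire, the number of PRO baselines dated after randomization.
- Exclude those baselines from the main change-score analysis.
- Run a sensitivity analysis that includes them.

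No change to data collection is called for: accrual closed on November 29, 2019 (SAP 2.1), and altering the form timing in protocol Appendix IV would change nothing already collected. The cost is one sentence in 7.1, a short addition to 7.8 and a date check. A few women with late baselines may drop out of the main change-score analysis. If the date check finds none, the results do not change.

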7.2 Study Conduct

All intention-to-treat patients are included in the analysis of study conduct. Information will be tabulated by randomized treatment and pooled treatment.

7.2.1 Patient Disposition and Follow-up

- Number of patients randomized, treated with surgery, not treated with surgery, reason for not treated with surgery (**Table 1**)
- Number of alive patients (**Table 2**)
- Median (estimated by Kaplan-Meier method) and range (minimum and maximum) (**Table 2**) of the follow-up time (months) defined as time from the day of randomization (as recorded in centralized randomization file) to the last day the patient is known alive (LKA) as the last recorded date known alive or censored at the time of death and calculated as
$$[(\text{date of death or LKA} - \text{date of randomization}) + 1]/30.4375.$$

7.2.2 Accrual Patterns

- Number of patients randomized by cooperative group and center (**Table 3**)
- Number of patients by stratification factors at randomization (**Table 4**)
- Accrual of patients by calendar time pooled across two treatment arms (**Figure 1**)

7.2.3 Eligibility Violations/Protocol Deviations

Eligibility violations of inclusion or exclusion criteria are centrally reviewed by CCTG; a field (y/n) for eligibility status and reason for ineligibility is entered in the database. A major protocol violation (MPV) is defined as a deviation from the protocol, initiated by the center or the investigator, serious enough to mean that the patient's data contributes little, if any, information on the efficacy or toxicity of the regimen under study. MPVs are coded by CCTG based on its standard codes.

- Number of patients eligible, not eligible (**Table 5**)
- Reasons for ineligibility (**Table 5**)
- Major protocol violations: % for each type of violations (**Table 5**)

Deviations from randomization will be summarized as follows:

- Treatment as randomized versus as treated (**Table 6**)

7.3 Study Population

All intention-to-treat patients are included in the study population analyses. Information will be tabulated by randomized treatment and pooled treatments.

7.3.1 Patient Pretreatment Characteristics

- Age: median, minimum, maximum values; <65, ≥65 (**Table 7**)
- Race: White, Black or African American, Native Hawaiian or other Pacific Islander, Asian, Not reported (or refused), Unknown (**Table 7**)
- Body mass index (BMI): median, minimum, maximum values (**Table 7**)
- ECOG Performance Status: 0, 1, 2, 3, 4 (**Table 7**)

7.3.2 Pre-Treatment Pathological Diagnosis of Tumor

- Months from initial pathological diagnosis of cervical cancer to randomization: median, minimum, maximum values (**Table 8**)
- Diagnostic Procedure: LEEP, cone, cervical biopsy (**Table 8**)
- Histological type: squamous, adenocarcinoma, adenosquamous (**Table 8**)
- FIGO stage: IA2, IB1 (**Table 8**)
- Histologic grade: 1, 2, 3, not assessable (**Table 8**)

7.3.3 Tumor Description at Baseline

- Diagnostic Procedure: cervical biopsy, LEEP/cone (**Table 9**)
- Clinic visibility of lesion: yes, no (**Table 9**)
- Tumour thickness: median, min - max (**Table 9**)
- Depth of stromal invasion: median, min - max (**Table 9**)
- Lateral extension: ≤7.0mm, >7.0mm, not stated in report (**Table 9**)
- Presence of lymphovascular invasion: yes, no, not stated in report (**Table 9**)
- Resected margin involvement: yes, no, not stated in the report (**Table 9**)
- Margin(s) involved: exocervical, endocervical, deep, unknown
- Presence of intra-epithelial lesion: yes, no, not stated in report (**Table 9**)

7.3.4 Results of Pelvic Exam and Imaging Tumor at Baseline

- Pelvic exam results: normal, abnormal-not malignant, abnormal-malignant (**Table 10**)
- Maximum dimension for malignant tumor: median, min-max values (**Table 10**)

- Detection of disease in pelvic imaging: yes, no, not applicable (**Table 10**)
- Location of tumour: cervix, lymph node, other (**Table 10**)
- Percentage of stroma involved: <50%, ≥50% (**Table 10**)
- Maximum tumour dimension: ≤20mm, >20mm (**Table 10**)

7.3.5 Baseline Symptoms and Major Medical Problems

- Baseline symptom status (**Table 11**)
- Number of patients with past or current major medical problems ongoing at baseline (**Table 12**)
- Type of major medical problem (**Table 12**)

7.3.6 Tobacco Smoking History

- Ever smoked any tobacco product: yes, no (**Table 13**)
- Current smoker: yes, no (**Table 13**)
- Current average cigarettes per day: median, min-max (**Table 13**)
- Time from quitting smoking to randomization: median, min-max (**Table 13**)
- Smoking history: pipe or cigar smoker only, 100 or fewer cigarettes during lifetime, greater than 100 cigarettes during lifetime (**Table 13**)
- Time from beginning of smoking cigarettes to randomization: median, min-max (**Table 13**)
- Total number of years smoked cigarette: median, min-max (**Table 13**)
- Average number of cigarettes smoked per day: median, min-max (**Table 13**)
- Pack years: median, min-max (**Table 13**)

7.4 Treatment Information

All treated patients as defined in Section 6 will be included in the analysis based on the type of surgery received by the patients.

7.4.1 Hysterectomy Procedure

- Procedure performed: hysterectomy with parametrium, hysterectomy with no parametrium, unilateral/bilateral salpingectomy, unilateral/bilateral oophorectomy, vaginal cuff (**Table 14**)
- Length of vaginal cuff: median, min-max (**Table 14**)
- Type of surgical approach: abdominal, laparoscopic, vaginal, robotic (**Table 14**)
- Total time of hysterectomy: median, minimum and maximum values (**Table 14**)

